### **9.4.2       Other analyses**

Individual PK results will be presented in listings and summarized using descriptive statistics.

Pharmacodynamic endpoints will be presented in listings and summarized at each scheduled assessment time point.

## **9.5       Handling of protocol deviations**

Important protocol deviations are deviations from the protocol which could potentially have a meaningful impact on study conduct or on the key safety, efficacy, or other outcomes for an individual study participant. The criteria for identifying important protocol deviations and the classification of important protocol deviations will be defined within the Important Protocol Deviations Template. To the extent feasible, rules for identifying protocol deviations will be

defined without review of the data and without consideration of the frequency of occurrence of such deviations. Whenever possible, criteria for identifying important protocol deviations will be implemented algorithmically to ensure consistency in the classification of important protocol deviations across all study participants.

All important protocol deviations will be listed by study participant.

A listing of all important protocol deviations related to the COVID-19 pandemic will be provided. Additionally, this listing will be repeated by during and post- the COVID-19 pandemic (in case the pandemic ends before the study is complete) based on the deviation start dates relative to the pandemic cutoff dates.

## **9.6 Handling of dropouts or missing data**

For secondary efficacy analyses, missing data will be handled according to the secondary efficacy estimand definition:

- For missing data of participants who discontinue from the study, a missing at random assumption will be used for imputation. This is in relation to the assumption that the participant had remained on their treatment throughout the study.
- For other missing data, the same missing at random assumption as the one used for imputing missing data of participants who discontinue from the study will be applied.

Missing or partial dates for safety evaluations will be imputed and full details of these algorithms will be presented in the SAP. Baseline is defined as the last nonmissing pretreatment measurement (Section 9.2). Therefore, data from the Screening Visit (if available) will be used as Baseline values if data are missing at Day 1.

No further imputations of any other missing data are planned.

## **9.7 Planned interim analysis and data monitoring**

If ZLP is not commercially available in the US at the time of the last visit of the last participant in the Main Treatment Period, an interim analysis will be conducted. This interim analysis will include all data collected during the Main Treatment Period.

## **9.8 Determination of sample size**

The secondary efficacy estimand will investigate if the Week 12 MG-ADL score is noninferior to the Baseline MG-ADL score with an NI margin of 2. It is assumed that the Week 12 CFB has an SD of 3 and that the true CFB is 0. Given a sample size of 20 study participants, the study has approximately 80% power to detect this, based on a 1-sided alpha of 0.025.

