### **Number of participants**

Twenty study participants are planned to be enrolled in the study.

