## 4 STUDY DESIGN

### 4.1 Overall design

MG0017 is a Phase 3b, multicenter, open-label, single-arm study to evaluate the safety, tolerability, and efficacy of ZLP in study participants with gMG switching from their current IV C5 inhibitor to SC ZLP.

To be eligible to participate in this study, participants must be adults ( $\geq 18$  years of age) with a documented diagnosis of gMG (Myasthenia Gravis Foundation of America [MGFA] Class II-IVa), currently receiving an IV C5 inhibitor approved for the treatment of gMG for at least 3 months (for eculizumab) or 4 months (for ravulizumab) prior to Screening (with the last dose being administered at the Screening Visit  $\pm 3$  days), considered to have a clinically stable disease as per the Investigator's judgment prior to Screening, and willing to switch from their current IV C5 inhibitor to SC ZLP.

The planned enrollment is 20 study participants in the US.

The study includes a 2-week or 8-week Screening Period (for participants receiving eculizumab or ravulizumab, respectively), a 12-week Main Treatment Period, and an optional Extension Treatment Period. A SFU Visit should be performed 40 days ( $\pm 7$  days) after the last dose of study medication (Section 6.8, Section 1.2).

The Screening Visit should be scheduled to coincide with the regularly scheduled study participant's IV C5 inhibitor administration ( $\pm 3$  days). Up to and including the time of the Screening Visit, study participants will continue to receive their IV C5 inhibitor at the recommended dose regimen. The last regularly scheduled IV C5 inhibitor administration cannot occur beyond Day -14 ( $\pm 3$  days) of the Screening Period for study participants receiving eculizumab or beyond Day -56 ( $\pm 3$  days) of the Screening Period for study participants receiving ravulizumab to ensure approximately a 2-week or 8-week interval between the last regularly scheduled IV C5 inhibitor administration (administered at the Screening Visit  $\pm 3$  days) and the first SC ZLP administration at the Baseline Visit, respectively.

At the end of the Screening Period and in case of no more than a 2-point change in study participants' MG-ADL score compared to the Screening Visit, study participants will enter the Main Treatment Period and will switch to SC ZLP (IV C5 inhibitor should not be administered after the Screening Visit). On Day 1, study participants will receive ZLP 0.3mg/kg administered

---

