## 7.2 Participant discontinuation/withdrawal from the study

Study participants are free to withdraw from the study at any time, without prejudice to their continued care.

A study participant may withdraw from the study at any time at his/her own request or may be withdrawn at any time at the discretion of the Investigator for safety, behavioral, compliance, or administrative reasons.

If the study participant withdraws consent for disclosure of future information, the Sponsor may retain and continue to use any data collected before such a withdrawal of consent.

If a study participant withdraws from the study, he/she may request destruction of any samples taken and not tested, and the Investigator must document this in the site study records.

See the Schedule of Activities (Section 1.3) for data to be collected at the time of study discontinuation.

Participants should be withdrawn from the study if any of the following events occur:

1. Participant develops an illness that would interfere with his/her continued participation.
2. Participant is noncompliant with the study procedures or medications in the opinion of the Investigator.
3. Participant restarts administration of previous IV C5 inhibitor or is administered a different IV C5 inhibitor (Section 6.5.2).
4. Participant withdraws his/her consent.
5. The Sponsor or a regulatory agency requests withdrawal of the participant.
6. Participant has active suicidal ideation with some intent to act without specific plan, as indicated by a positive response (“Yes”) to question 4 of the “Since Last Visit” version of the C-SSRS. The participant should be referred immediately to a mental healthcare professional and may be withdrawn from the study based upon the Investigator’s judgment of benefit/risk of continuing the participant in the study/on study medication.

7. Participant has active suicidal ideation with a specific plan as indicated by a positive response (“Yes”) to question 5 of the “Since Last Visit” version of the C-SSRS. The participant should be referred immediately to a Mental Healthcare Professional and must be withdrawn from the study.

Investigators should contact the Medical Monitor, whenever possible, to discuss the withdrawal of a study participant in advance.

If a study participant withdraws from the study, the participant will not be replaced.

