### **9.1 Definition of analysis sets**

The following are the defined analysis sets:

- Enrolled Set (ES): The ES will include all study participants who signed the ICF.
- Intention-to-Treat (ITT) Population: The ITT Population will include all eligible study participants. Efficacy analyses will be performed on the ITT in case there is a difference of at least 5 participants as compared to the modified Intention-to-Treat (mITT) Population.
- Modified ITT Population: The mITT Population will include all eligible study participants who received at least 1 post-Baseline dose of study medication and had at least 1 post-Baseline assessment. The mITT Population will be used for all efficacy analyses.
- Safety Set (SS): The SS will include all study participants who received at least 1 dose of study medication and will be used for the demography and safety analyses.
- Pharmacokinetic Per-Protocol Set (PK-PPS): The PK-PPS will include all study participants in the safety population who received at least 1 dose of study medication and had at least 1 quantifiable PK measurement postdose of study medication without important protocol deviations that would affect the PK. The PK-PPS will be used for all PK analyses.
- Pharmacodynamic Per-Protocol Set (PD-PPS): The PD-PPS will include all study participants in the safety population who received at least 1 dose of study medication and had at least 1 quantifiable PD measurement postdose of study medication without important protocol deviations that would affect the PD. The PD-PPS will be used for all PD analyses.

Additional detail about analysis sets will be provided in the SAP.

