### **10.1.3 Informed consent process**

Study participant's informed consent must be obtained and documented in accordance with local regulations, ICH-GCP requirements, and the ethical principles that have their origin in the principles of the Declaration of Helsinki.

Prior to obtaining informed consent, information should be given in a language and at a level of complexity understandable to the study participant in both oral and written form by the Investigator (or designee). Each participant will have the opportunity to discuss the study and its alternatives with the Investigator.

Prior to participation in the study, the ICF should be signed and personally dated by the study participant, or his/her legal representative, and by the person who conducted the informed consent discussion (Investigator or designee). The study participant or his/her legal representative must receive a copy of the signed and dated ICF. As part of the consent process, each study participant must consent to direct access to his/her medical records for study-related monitoring, auditing, IRB review, and regulatory inspection.

If the ICF is amended during the study, the Investigator (or the Sponsor, if applicable) must follow all applicable regulatory requirements pertaining to the approval of the amended ICF by the IRB and use of the amended form.

All studies conducted at centers in the US must include the use of a Health Insurance Portability and Accountability Act authorization form.

The participant may withdraw his/her consent to participate in the study at any time. A participant is considered as enrolled in the study when he/she has signed the ICF. An eCRF must not be started, nor may any study specific procedure be performed for a given participant, without having obtained his/her written consent to participate in the study.

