Section 5.1.1.3.1 Study periods for safety and efficacy data	
Added underlined text for the Safety Follow Up (SFU) Period during the Main Treatment Period:
 
SFU Period: 40 days (after the last dose for patients who do not enter the extension period or do not transition to commercially available ZLP directly after the Week 12 visit).	To define the rules for the participants to enter the period uniformly across the section.
Section 5.1.1.4 Mapping of assessments performed at (Early) Withdrawal Visit	
Section title was updated from:
 
Mapping of assessments performed at Early Discontinuation Visit,toMapping of assessments performed at (Early) Withdrawal Visit	Early discontinuation visit is not defined based on the study protocol
Section 5.1.1.7.3 Missing data due to COVID-19	
Added clarification that the protocol deviations related to COVID-19 will be documented only in listings.	
COVID-19 related protocol deviations are mostly related to missed visits due to COVID-19 social restrictions or COVID-19 infections; currently the pandemic period is over and only limited such PD occurrences are expected;

	
 Below text is deleted: If the WHO declares an end to the pandemic prior to the end of the study, included additional summary analyses based on the COVID-19 pandemic period (during/post). 	
data can be documented only in listings.
 
 By the time WHO declared the end of the pandemic period (05 May 2023) 5 out of the 20 patients had entered the study. During the end of the pandemic period COVID-19 social restrictions had been removed; summaries could not be affected by COVID-19 outbreak at the time being.

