5.2 Participant Dispositions

The following summaries will be created.

- **Reasons for screen failures** will be summarized using the ES.
- **Disposition of analysis sets** will be summarized overall, by analysis sets (ES, ITT, mITT, SS, PK-PPS, PD-PPS). Percentages will be based on the number of participants in the ES overall. Disposition of analysis sets will also be summarized in the ES by region, with number of sites, principal investigator name, dates of first participant in and last participant out as well as the number of participants screened/screen failures.
- **Disposition and discontinuation reasons** using mITT population will contain the number and percentage of study participants who started, completed, permanently discontinued the Main Treatment Period with primary reason of discontinuation, and entered, completed, permanently discontinued the Extension Treatment Period with primary reason of discontinuation. Percentages will be based on the number of participants in the mITT population. This summary will be performed for the Main Treatment Period as well as for the Overall Treatment Period. The disposition and discontinuation reasons will be duplicate in the ES in case there is a difference of strictly more than 5 patients between the ES and the ITT.
- **Discontinuation due to AEs** using mITT population will summarize the total number of study participants who discontinued the study due to AEs by the categories: AE, serious fatal, and AE, non-fatal. This summary will be performed for the Main Treatment Period as well as for the Overall Treatment Period. The discontinuation due to AEs will be duplicate in the ES in case there is a difference of strictly more than 5 patients between the ES and the ITT.
- **Impact of COVID-19** using the mITT will summarize number and percentage of participants in each impact category by visit. This table will be done overall. Visits and assessments done via video calls will be listed. For both the listing and the summary table, only visits at which efficacy or safety assessments are scheduled will be included. This summary will be performed for the Main Treatment Period as well as for the Overall Treatment Period. The impact of COVID-19 will be duplicate in the ES in case there is a difference of strictly more than 5 patients between the ES and the mITT.

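### Does the stated 80% power for 20 participants fail because the plan allows for no losses and counts its 20 as people who signed consent?

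*Protocol*

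**What the plan says.** Protocol 9.8, repeated in SAP 3, bases the sample size on the secondary efficacy test of MG-ADL change from Baseline to Week 12 against a margin of 2. It assumes an SD of 3, a true change of 0 and a one-sided alpha of 0.025, and concludes: "Given a sample size of 20 study participants, the study has approximately 80% power to detect this". Neither section mentions dropout or missing data. Protocol 7.2 adds: "If a study participant withdraws from the study, the participant will not be replaced".

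On who the 20 are, the Protocol synopsis says "Twenty study participants are planned to be enrolled in the study" and Protocol 4.1 says "The planned enrollment is 20 study participants in the US". Protocol 10.1.3 states: "A participant is considered as enrolled in the study when he/she has signed the ICF". Protocol 9.1 matches this for the Enrolled Set: "The ES will include all study participants who signed the ICF". In SAP 5.2, reasons for screen failure "will be summarized using the ES", so screen failures are members of that set. The rationale for SAP Amendment 2.0, giving the position when the pandemic was declared over, says that "5 out of the 20 patients had entered the study".

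**The concern.** There are two worries. First, the power is quoted as if all 20 participants supply a Week 12 value, with nothing held back for losses and no replacement. In a study where people leave a treatment on which they are stable, some withdrawal is foreseeable: Protocol 7.2 itself lists a return to an IV C5 inhibitor as a reason for withdrawal.

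Second, if the 20 are consent signers, some will fail screening. Inclusion criterion 6 (MG-ADL stability) is checked only at Baseline, 2 or 8 weeks after the Screening Visit. Those people never reach the mITT Population used for efficacy, and recruitment could in principle stop at 20 consents.

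This is the only formal hypothesis test in the study. A failure to show noninferiority would be read against a nominal 80% that the study might not have had.

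**Working it through.** **Inputs (Protocol 9.8, SAP 3):** margin 2, SD 3, true change 0, one-sided alpha 0.025, n = 20. Test: one-sample t (Protocol 9.3.1).

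**1. The plan's own figure.** Power = P(T > t(0.975, n−1)), where T is noncentral t with n−1 degrees of freedom and noncentrality 2√n/3. At n = 20 the noncentrality is 2 × 4.472/3 = 2.981, the critical value is 2.093 and the power is 0.8073. The stated figure reproduces.

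**2. Participants who contribute nothing.** The loss counts are assumptions.

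| Contributing at Week 12 | Noncentrality | Critical t | Power |
|---|---|---|---|
| 20 | 2.981 | 2.093 | 80.7% |
| 19 | 2.906 | 2.101 | 78.5% |
| 18 | 2.828 | 2.110 | 76.0% |
| 16 | 2.667 | 2.131 | 70.3% |

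So 20 is the smallest n at or above 80%. At n = 20 the largest SD that still gives 80% is 3.028.

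**3. Participants dosed but lost before Week 12.** SAP 5.3.1.1.2 uses an MMRM on Weeks 1, 2, 4, 8 and 12, under missing at random. As an approximation, take 20 dosed, m with Week 12 data, and one earlier visit correlated ρ with Week 12:

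variance = 9 × [(1−ρ²)/m + ρ²/20], effective n = 9/variance, df = m−1.

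- m = 18: ρ = 0.5 gives effective n 18.46 and power 77.0%; ρ = 0.8 gives 19.23 and 78.7%.
- m = 16: ρ = 0.5 gives effective n 16.84 and power 72.5%; ρ = 0.8 gives 18.35 and 76.1%.

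The correlations are assumed; the documents give none. In addition, SAP 5.1.1.1.4 maps early-withdrawal assessments to the next scheduled visit. MG-ADL is scheduled at Weeks 8 and 12, so someone who withdraws after Week 8 and attends that visit still supplies a Week 12 value.

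**4. Baseline adjustment.** The MMRM includes baseline MG-ADL. If its correlation with the change is r, the residual SD is 3√(1−r²), with df about n−2. For an assumed r = 0.3 the residual SD is 2.862, and the nominal power is 84.0% at n = 20 and 79.5% at n = 18. This should not be leaned on. In a single arm with complete data, the adjusted mean at the average baseline is simply the mean change, so the gain comes from a smaller reported standard error and not from a more precise estimate.

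**5. Who the 20 are.** The passages point two ways.

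- *Consent signers:* the synopsis and Protocol 4.1, read with the definitions in 10.1.3 and 9.1.
- *Entrants:* the power sentence refers to study participants and not to the Enrolled Set. Protocol 5.4 describes screen failures as people who consent but do not go on to enter. Appendix 4 (Section 10.4) requires menopausal status to be confirmed before enrolment, which uses that word for a step after screening. The SAP amendment rationale counts progress towards 20 in people who had entered.

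The second reading fits the calculation and the sponsor's own count. The conflict is confined to the word enrolled.

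**The case for a change.** The best case for a change is that it would cost almost nothing: a sentence saying that the 20 are people who start study medication and that the power assumes complete Week 12 data. The MMRM cannot help with people who are never dosed, and SAP 5.3.1.1.4 keeps an observed-data t-test at Week 12, to which the figures in step 2 apply directly. The amendment rationale shows intent but does not correct the definition in Protocol 10.1.3.

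What stands is that the assumption of no missing data is unstated and that the two uses of enrolled do not agree. Two participants with no data would also take the power outside what most people would call about 80%.

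What does not stand is the claim that the stated power holds only with zero loss. That is true of a strict 80% threshold; the plan says approximately, and 78.5% with one full loss still fits. The documents give no loss rate, so no shortfall can be shown. Nor could the 20 safely be defined as mITT members: that set requires a post-Baseline assessment, and with no replacement recruitment cannot guarantee it.

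**Conclusion.** The concern does not call for a change. The stated power is correct for the stated number: 80.7% by exact calculation. The missing loss allowance is an unstated assumption and not an error, and anyone interpreting a failed test can work out the power from the number who actually contributed. The enrolled wording is a clerical inconsistency, and the surrounding text points to 20 entrants.

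The possible shortfall is conditional. It is about 2 points for one participant with no data, about 5 for two and about 10 for four, and somewhat less for dosed participants whose visits before Week 12 enter the MMRM. These sizes rest on the plan's SD of 3 and true change of 0, and on loss counts and visit correlations that the documents do not supply. The test is secondary; the primary endpoints are safety incidences. Writing the assumption down would leave the sample size, the analysis, the decision rule and the result as they are.

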## **10 SUPPORTING DOCUMENTATION AND OPERATIONAL CONSIDERATIONS**

### **10.1 Appendix 1: Regulatory, ethical, and study oversight considerations**

#### **10.1.1 Regulatory and ethical considerations**

The study will be conducted under the auspices of an IRB, as defined in local regulations, International Council for Harmonisation (ICH)-Good Clinical Practice (GCP), and in accordance with the ethical principles that have their origin in the Declaration of Helsinki.

The Investigator/UCB will ensure that an appropriately constituted IRB that complies with the requirements of the current ICH-GCP version or applicable country-specific regulations will be responsible for the initial and continuing review and approval of the clinical study. Prior to initiation of the study, the Investigator/UCB will forward copies of the protocol, ICF, IB, Investigator's curriculum vitae (if applicable), advertisement (if applicable), and all other participant-related documents to be used for the study to the IRB for its review and approval.

Before initiating a study, the Investigator will have written and dated full approval from the responsible IRB for the protocol.

The Investigator will also promptly report to the IRB all changes in the study, all unanticipated problems involving risks to study participants or others, and any protocol deviations, to eliminate immediate hazards to study participants.

The Investigator will not make any changes in the study or study conduct without IRB approval, except where necessary to eliminate apparent immediate hazards to the study participants. For minor changes to a previously approved protocol during the period covered by the original approval, it may be possible for the Investigator to obtain an expedited review by the IRB as allowed.

As part of the IRB requirements for continuing review of approved studies, the Investigator will be responsible for submitting periodic progress reports to the IRB (based on IRB requirements), at intervals appropriate to the degree of study participant risk involved, but no less than once per year. The Investigator should provide a final report to the IRB following study completion.

UCB (or its representative) will communicate safety information to the appropriate regulatory authorities and all active Investigators in accordance with applicable regulatory requirements. The appropriate IRB will also be informed by the Investigator or the Sponsor, as specified by the applicable regulatory requirements. Where applicable, Investigators are to provide the Sponsor (or its representative) with evidence of such IRB notification.

